2.5 Part 4: Dose and Schedule Evaluation

The dose and schedule evaluation segment will consist of approximately 21 evaluable ES patients.

All patients in the dose and schedule evaluation segment will receive a starting dose of 175 mg/m²/day of TK216 intravenously by continuous infusion for 28 days per cycle.

If the patient's tumor response as determined by the Investigator is inadequate after at least one protocol-specified post-baseline assessment and they are not experiencing toxicities at this dose level, the Investigator may increase the dose to 200 mg/m²/day after discussion with the Sponsor.

Vincristine may be administered in parallel with the TK216 infusion following progressive disease after TK216-01 monotherapy but only after consultation with the Sponsor.

2.6 Dose modification:

TK216 dose or schedule reduction for patients may be warranted after Cycle 1 as a consequence of drug-related toxicities. Dose reduction will be documented in the CRF along with reason for reduction. The decision to reduce the dose will be made by the Investigator, who may consult with the Sponsor if indicated.

Vincristine dosing will be interrupted for any clinically intolerable neuropathy (e.g., grade 4 foot drop, severe paresis, disabling paresthesias or ileus), and may be resumed if the neuropathy becomes clinically tolerable. If seizures occur the vincristine dosing should be interrupted until seizure activity is controlled and may be resumed if antitumor responses warrant in the opinion of the Investigator. In either case, the subsequent vincristine dose should be 0.75 mg/m². If the total bilirubin increases to greater than 1.9 mg/dL, vincristine dosing should be stopped. If the total bilirubin is between 1.5 – 1.9 mg/dL then vincristine should be administered at 0.75 mg/m².

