Hematology toxicities	
 Grade 4 neutropenia (absolute neutrophil count [ANC] < 500/mm³) lasting >7 days; Grade 4 anemia; Febrile neutropenia (ANC <1000/mm³ with a single temperature of > 38.3 °C or a sustained temperature of ≥ 38 °C for more than one hour); Grade ≥ 3 neutropenic infection (i.e., infection documented clinically or microbiologically with grade ≥ 3 neutropenia); Grade 4 thrombocytopenia (platelet count < 25,000/mm³); Grade 3 thrombocytopenia (platelet count < 50,000-25,000/mm³) lasting >7 days or associated with clinically significant bleeding.
Gastrointestinal toxicities	
 All ≥ Grade 4 vomiting or diarrhea; Grade 3 nausea or vomiting despite optimal antiemetic therapy that fails to recover to at least Grade 2 within 72 hours; Grade 3 diarrhea despite optimal management of the event that fails to recover to at least Grade 2 within 72 hours.
CNS toxicities	
 Grade ≥ 3
Other non-hematological toxicities	
 Grade ≥ 3; Grade 2 increase in AST/ALT in combination with a grade 2 increase in bilirubin; For patients with liver metastases with elevated liver transaminases at baseline (2.5-5x ULN), DLT shall be defined as a doubling of the baseline liver transaminase value(s); Toxicity of any grade that interrupts the first seven day infusion for ≥24 hours.
Failure to recover (except alopecia)	
 Failure to recover to Grade ≤ 2 toxicity or to baseline values after delaying the initiation of next cycle by a maximum of 21 days

Patients are eligible for DLT evaluation if they experience a DLT after receiving any amount of study drug or do not experience a DLT having taken a minimum of 85% of dose expected during the first cycle. Patients who do not fulfill these requirements and those who discontinue study participation prior to completing the first cycle will be replaced.

The MTD is the dose level at which 0 of 6 or 1 of 6 patients experience first-cycle DLT, and at least 2 of 3 or 2 of 6 patients experience first-cycle DLT at the next higher dose level. Effectively, the MTD is the highest dose associated with first-cycle DLT in < 33% of patients.

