2.3 Part 2 Schedule Escalation Segment

Once the MTD for patients receiving TK216 by continuous infusion for seven days has been identified, the tolerability of longer infusion times will be determined.

This segment will also be performed in sequential cohorts of patients receiving TK216 intravenously by continuous infusion via a central venous catheter. A "3+3" patient enrollment scheme will be followed during the schedule escalation. If 2 of 3 patients experience a first-cycle DLT then accrual to the cohort will cease, and the subsequent cohort will receive TK216 at the next lower dose. If a first-cycle DLT is seen in one of the 3 patients in a cohort, that cohort will enroll an additional 3 patients. DLT is defined as an adverse event occurring during the first cycle that is at least possibly related to TK216 and meets the DLT definition for the schedule escalation segment (Table 2). When 0 of 3, or 1 of 6 patients in a cohort experience first cycle DLT, the dose will be escalated in the subsequent cohort.

The starting daily dose level in the schedule escalation segment will be the MTD determined in the Part 1 dose escalation segment as described in the previous section.

The first schedule escalation cohort will receive TK216 by continuous IV infusion for 10 days.

The selection of dose and schedule for subsequent cohorts will be made by the Investigators and Sponsor after evaluating the first cycle results of the previous cohort. The dose level for newly enrolled patients will be assigned by Oncternal Therapeutics, Inc. at the time of registration.

By way of illustration:

- If 0 of 3 or 1 of 6 patients in the first dose escalation experience first cycle DLT, the second schedule escalation cohort will receive TK216 by continuous IV infusion at the same dose for 14 days.
- If 2 or more patients in the first dose escalation experience first cycle DLT, the second schedule escalation cohort will receive TK216 by continuous IV infusion at the next lower dose for 10 days.

The same decision algorithm will be used to select the dose and schedule for the third and subsequent schedule escalation cohorts.

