It is anticipated that 4 to 6 cohorts will be completed during the schedule escalation segment of this trial. With the concurrence of the investigators and the study sponsor, further testing may be performed in up to 12 additional patients per dose level to refine the estimation of the MTD and RP2D at intermediate dose levels or to define a higher MTD and RP2D while using Cycle 1 primary supportive care prophylaxis (e.g., with growth factors, antidiarrheals, antiemetics) for bone marrow and/or gastrointestinal toxicities.

The duration of cycles will be variable. Following the scheduled infusions of TK216, a rest period will begin. The next cycle for a patient may begin as soon as all the patient's toxicities attributed to TK216 have resolved to less than Grade 3, or are clinically tolerable Grade 3 toxicities.

Once a patient completes Cycle 2 of any schedule escalation cohort, vincristine can be administered on Day 1 of a subsequent cycle and on Day 1 of each subsequent cycle. The initial dose of vincristine on Day 1 of the starting cycle will be 0.75 mg/m² given via intravenous infusion prior to the initiation of the TK216 infusion. Subsequent doses beginning on Day 1 of the next cycle and beyond will be 1.5 mg/m² up to a maximum dose of 2 mg.

Additional cycles of therapy may be administered provided that the patient meets the following criteria on Day 1 of each cycle:

- ANC \geq 1,000/mm³
- Hemoglobin \geq 8.0 gm/dL (Blood transfusions are permitted.)
- Platelets \geq 50,000/mm³
- Non-hematologic toxicity(s) recovered to less than Grade 3, or are clinically tolerable Grade 3 toxicities
- In patients receiving vincristine, clinically tolerable neurotoxicity, and lack of seizure activity

A rest period of 14 days is required following the first cycle, but the rest period may be reduced following subsequent treatments if the above criteria are met.

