If TK216 treatment has been well tolerated in Cycle 1 and 2, starting in Cycle 3 the duration of the TK216 infusion may be increased (e.g. from 14 to 17 or 14 to 21 days). If the longer infusion is well tolerated, the duration of the TK216 infusion may be increased further in subsequent cycles. There is no maximum treatment duration. If a longer infusion time is not well tolerated, the patient may remain on study, but receive a shorter duration of TK216 infusion in the next treatment cycle. The assessments noted for Days 8+/-1 and 15+/-1 in the Section 16.3 Schedule of Events (Schedule Escalation and Expansion Cohorts) should be performed every 7-8 days during longer infusions (Adverse events, Concomitant medications, Vital signs, Symptom driven physical exam, Hematology, Clinical chemistry, Coagulation, Urinalysis, and Plasma for PK assessment). A complete blood count (CBC with differential) should be obtained approximately half way between the weekly assessment at the study center or local laboratory.

Patients may have their dose increased to the next dose level at the next cycle if any cycle of TK216 is

well-tolerated with no clinically significant toxicity greater than Grade 2 attributed to TK216. If TK216 treatment has been well tolerated in Cycle 1 and 2, starting in Cycle 3 the duration of the TK216 infusion may be increased, in consultation with the Sponsor.

Intra-patient dose increases will be permitted during the schedule escalation segment of this trial. If any cycle of TK216 is well tolerated with no clinically significant toxicity greater than Grade 2 attributed to TK216, then the daily dose of TK216 may be increased to the next dose level on the next cycle upon discussion with the sponsor. No cycle should initiate:

1. Both vincristine for the first time and have a dose increase, or
2. Both vincristine for the first time and have an increase in the length of TK216 infusion, or
3. Increase the length of infusion for the first time and have a dose increase.

After the RP2D has been determined (recommended dose and schedule), an expansion cohort will be enrolled.

Table 2 Dose Limiting Toxicity – Part 2 Schedule Escalation Segment

Category	Criteria

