Hematology toxicities	
 • Grade 4 neutropenia (absolute neutrophil count [ANC] < 500/mm³) lasting more than 7 days; • Grade 4 neutropenic fever: life-threatening consequences, urgent intervention indicated • Grade 4 thrombocytopenia (platelet count < 25,000/mm³) lasting more than 7 days; • Clinically significant thrombocytopenic bleeding;
Non-hematological toxicities	
 • Any ≥ Grade 3 toxicity that is not clinically tolerable; • For patients with liver metastases with elevated liver transaminases at baseline (2.5-5x ULN), DLT shall be defined as a doubling of the baseline liver transaminase value(s).
Failure to recover (except alopecia)	
 • Failure to recover to a clinically tolerable level of any toxicity attributed to TK216

Patients are eligible for DLT evaluation if they experience a DLT after receiving any amount of study drug or do not experience a DLT having taken a minimum of 85% of dose expected during the first cycle. Patients who do not fulfill these requirements and those who discontinue study participation prior to completing the first cycle will be replaced.

The RP2D may be determined by the MTD or optimal target inhibition with an acceptable safety profile.

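### Part 4, in the text shown, defines no DLT and sets no toxicity count that requires a review before more patients start at 175 mg/m²/day

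*Combined protocol and SAP*

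**What the plan says.** **Part 4 regimen.** Section 2.5: "The dose and schedule evaluation segment will consist of approximately 21 evaluable ES patients", and "All patients in the dose and schedule evaluation segment will receive a starting dose of 175 mg/m²/day of TK216", infused over 28 days per cycle. Section 3.1 admits Cohort 11 from age 8, against 10 for Cohorts 6 to 10. Section 4.2.4.6 requires no rest, and section 4.2.4.5 lets Day 28 double as Day 1 of the next cycle.

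**Part 4 safety rules.** These act on the individual patient: hold, resume, or reduce to 145 and then 130 mg/m²/day (2.6.2); G-CSF and ANC holds (2.6.4); Day 1 criteria for each further cycle (4.2.4.1). The only numerical criterion for the cohort is 4 responses in 21 (9.3).

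**Earlier parts.** Part 1 has Table 1, 3+3 counts and a stated limit: "Effectively, the MTD is the highest dose associated with first-cycle DLT in < 33% of patients". Part 2 has Table 2 and 3+3 counts, and "The selection of dose and schedule for subsequent cohorts will be made by the Investigators and Sponsor after evaluating the first cycle results". It names first-cycle infusions of 10 and then 14 days, and "A rest period of 14 days is required following the first cycle". Part 3 (2.4) applies Table 2 to a vincristine run-in; two or more DLTs in the first six lead to revised vincristine and/or TK216 dosing.

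**General oversight.** SAEs are reported within one working day and SUSARs are expedited (4.1.7.4). The sponsor passes new safety information to investigators, who inform the IRB/IEC (8.3). The sponsor may stop the study at any time (8.7).

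**The concern.** A hold or reduction protects the patient who already has the toxicity. It does not settle whether the next patient should start at the same dose and length. In Parts 1 and 2 a DLT count answers that question; in the visible Part 4 text nothing does. Section 9.4 plans to present DLTs by dose group, but without a Part 4 definition there is nothing agreed to count.

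Part 4 is also where such a count would be useful. Every patient has 28 infusion days in the first cycle, the required rest is dropped, and 8- and 9-year-olds become eligible. In Parts 2 and 3, longer infusions within a patient were allowed from Cycle 3, after Cycles 1 and 2 had been well tolerated. Experience gained that way comes from patients selected for tolerance. At stake is how many patients, children among them, start a poorly tolerated regimen before anyone is obliged to look at the cohort as a whole.

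**Working it through.** **1. The plan's own figures.** For 4 or more responses in 21, the exact binomial gives a one-sided α of 0.0189 at an ORR of 5% and power of 0.808 at 25%. This agrees with section 9.3 (0.025 and 80%). The 3+3 table uses (1−p)³ + 3p(1−p)² × (1−p)³. At p = 0.3 this is 0.343 + 0.151 = 0.494, against 0.49 printed, and the other entries match. The point is therefore an absent rule, not a wrong number.

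**2. What exists for Part 4.**

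| Element | Part 1 | Part 2 | Part 3 | Part 4 (text shown) |
|---|---|---|---|---|
| DLT definition | Table 1 | Table 2 | Table 2, vincristine run-in | none |
| Cohort toxicity count | 3+3 | 3+3 | 2 of first 6, run-in only | none |
| Patient-level holds and reductions | yes | yes | yes | yes |

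**3. First-cycle length.** 28/14 = 2.0 times the longest first-cycle infusion named in Part 2. This compares infusion days only. It is not a ratio to the longest infusion given, which the text does not report.

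**4. How a 2-of-6 trigger would behave.** Two in six is 33.3%, just outside the protocol's limit of below 33%. Let p be the true first-cycle DLT rate, equal and independent across patients. The documents give no p for this schedule, so the range is assumed.

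P(review) = 1 − (1−p)⁶ − 6p(1−p)⁵. At p = 0.3: 1 − 0.118 − 0.303 = 0.580.

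| True DLT rate p | P(review) | P(no review) | 3+3 does not escalate (1 − printed value) |
|---|---|---|---|
| 10% | 0.114 | 0.886 | 0.09 |
| 20% | 0.345 | 0.655 | 0.29 |
| 30% | 0.580 | 0.420 | 0.51 |
| 33.3% | 0.649 | 0.351 | not printed |
| 40% | 0.767 | 0.233 | 0.69 |
| 50% | 0.891 | 0.109 | 0.83 |

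I do not convert this into patients spared. The review can fall due at the second DLT, before six have started, and the number already started depends on accrual speed, which is not given.

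**5. Carrying Table 2 to a 28-day cycle.** Grade 4 neutropenia or thrombocytopenia counts only if it lasts more than 7 days. An event starting near Day 28 therefore needs follow-up to about Day 36 (28 + 8). Table 2 also lists "Failure to recover to a clinically tolerable level of any toxicity attributed to TK216" with no time limit.

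The Part 2 evaluability rule keeps DLT-free patients only if they "do not experience a DLT having taken a minimum of 85% of dose expected during the first cycle". For 28 days, 0.85 × 28 = 23.8, so a hold of more than 28 − 23.8 = 4.2 days fails it if held days are not made up. The ANC rule in section 2.6.4 can produce such a hold. Replacing those patients would remove the ones who could not complete the cycle.

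**The case against.** **Part 4 has a different purpose.** Parts 1 and 2 look for DLTs; Part 4 estimates ORR. Part 3, also aimed at ORR, has a count only for adding vincristine, so it is limited precedent. This stands, and it is why the point is an improvement rather than an error.

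**A reader might infer that a 28-day first cycle had never been tested, or that 21 days was the ceiling.** The documents do not support this. Section 6.3.5.7 provides for patients still on infusion at Day 22, section 6.3.5.9 schedules a Day 22 PK sample if the infusion continues, and section 2.3 applies its algorithm to later cohorts without an upper limit on length. A gated 28-day first cycle in Part 2 was possible; the text does not say whether one took place. The regimen rationale, synopsis and section 16.3 are not shown.

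**A reader might infer that accrual would continue whatever toxicity appeared.** That also goes too far. SAE and SUSAR reporting, safety notices and the sponsor's right to stop all operate above the single patient. Part 4's non-hematologic Day 1 criterion is stricter than Part 2's, and visits are roughly weekly. What remains is that none of these names a level at which review is required.

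**Section 9.4 is not contradicted.** It presents DLTs as appropriate, so a part without them is not an inconsistency.

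**The trigger has costs.** At a true 30%, still within the protocol's limit, it calls a review 58% of the time. This stands. It is close to the 51% chance that the plan's own 3+3 rule declines to escalate at that rate, and the result is a review, not a stop. Lowering the starting dose would also depart from the primary objective, which is tied to 175 mg/m²/day.

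**Conclusion.** The gap holds at cohort level and for the text shown: Part 4 has no DLT definition and no toxicity count that requires a review before further starts at 175 mg/m²/day. Patient-level rules and sponsor oversight are in place, so this does not show Part 4 to be unmonitored or unsafe, and the 4-of-21 calculation is sound.

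The true DLT rate on this schedule is unknown, so any gain is conditional. A single 2-of-6 look prompts a review with probability 0.77 at a true 40% and 0.89 at 50%, and misses those rates with probability 0.23 and 0.11. If the pages not shown already contain a rule or first-cycle data for 28 days, a cross-reference in section 2.5 would be enough.

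**What to change.** Add to section 2.5:

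1. **Definition.** Table 2 applies to events with onset in the 28-day Cycle 1, followed for about 7 to 8 more days so that late Grade 4 cytopenias can be classified. For this count, judge failure to recover at the end of that window.
2. **Denominator.** Any treated patient with a DLT counts. A DLT-free patient whose dose falls below 85% because of a drug-related hold is not replaced, and is listed separately for the review as unable to complete the cycle. Without that listing, the patient would look like someone who tolerated 28 days.
3. **Trigger.** If a second DLT occurs among the first six patients, the sponsor and investigators review before further patients start at 175 mg/m²/day. They decide to continue, change supportive care, or lower the starting dose, for example to 145 mg/m²/day, already a reduction level in section 2.6.2.
4. **Analysis.** If the starting dose is lowered, report ORR by starting dose and apply the 4-of-21 rule only to patients started at 175 mg/m²/day. The stated power needs 21 such patients.

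**Cost.** Protocol wording and DLT classification for six patients by existing staff. Reviews will occur at acceptable rates (11%, 34% and 58% at 10%, 20% and 30%). Accrual may be delayed by about four to five weeks if the seventh patient waits for the sixth's window; otherwise a few more start before the count is known. One look at six does not cover later patients or later cycles.

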1.3 Part 3 Expansion Segment

The primary objective of the Part 3 expansion segment is ORR defined as Complete Response (CR) and Partial Response (PR) of the RP2D regimen of TK216 administered intravenously via continuous infusion through a central venous catheter in patients with relapsed or refractory ES. (includes patients with Ewing sarcoma family of tumors-ESFT). The RP2D regimen may include use of vincristine, a standard therapy for Ewing sarcoma.

Secondary objectives of the Expansion Cohort segment of the study are to assess:

- Progression-Free Survival (PFS) defined as time from first dose of TK216 to tumor progression or death due to any cause
- Overall Survival (OS) defined as time from first dose of TK216 to death due to any cause
- Duration of response (DOR) as defined from the first date a response is identified (either CR or PR) until the date of disease progression
- Disease Control (DC) defined as the proportion of patients with a confirmed Complete Response (CR), Partial Response (PR) or Stable Disease (SD)
- Duration of Disease Control defined as first date of disease control identified (either CR, PR or SD) until the date of progression
- Safety and tolerability of TK216 alone and combined with vincristine as characterized by Adverse Event type, severity, timing and relationship to study drug, as well as laboratory abnormalities
- Exploratory biomarker development to enable prediction of drug toxicity, tumor response and the mechanism(s) of acquired study drug resistance.
- Pharmacodynamics of TK216 on molecular targets in surrogate tissue
- Pharmacokinetics (PK) of TK216 alone and when combined with vincristine

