1.4 Part 4: Dose and Schedule Evaluation Segment

Primary Objective:

The primary objective of the Part 4 dose and schedule evaluations segment is to assess ORR defined as Complete Response (CR) and Partial Response (PR), per RECIST v1.1, at a starting dose of 175 mg/m²/day of TK216 administered intravenously via continuous infusion over 28-days in patients with relapsed or refractory Ewing Sarcoma.

Secondary Objectives:

- Duration of response (DOR) per RECIST v1.1
- Disease control rate (DCR) per RECIST v1.1
- Progression free survival (PFS) per RECIST v1.1
- Overall survival (OS)
- Safety and tolerability of TK216 alone as characterized by AE type, severity, timing and relationship to study drug, as well as laboratory abnormalities

- Pharmacodynamics of TK216; Exploratory biomarker development to enable prediction of drug toxicity, tumor response and the mechanism(s) of acquired study drug resistance
- Pharmacokinetics of TK216 alone

2. Study Design

TK216-01 is a multicenter, open-label, Phase 1/2 study in which the safety and efficacy of TK216 will be evaluated in patients with relapsed or refractory ES (including patients with ESFT).

Once an appropriate patient has been identified, a 30-day screening period will begin to evaluate eligibility using the defined study inclusion and exclusion criteria.

The study will be executed in several Parts:

- **Part 1:** Dose Escalation Segment (Cohorts 1-6)
- **Part 2:** Schedule Escalation Segment (Cohorts 7-9)
- **Part 3:** Expansion Segment (Cohort 10)
- **Part 4:** Dose and Schedule Evaluation Segment (Cohort 11)

All patients will be treated until objective tumor progression per RECIST v1.1., withdrawal of consent, unacceptable toxicity, study termination by sponsor, or a maximum of 2-years. Patients may receive supportive care for bone marrow and/or gastrointestinal adverse events (e.g., with growth factors, antidiarrheals, antiemetics) and prophylaxis for established toxicities that are recurrent.

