For the Part 3 expansion segment, the scan schedule will be at the end of every even-numbered cycle's rest period, and prior to starting the next infusion. The same methodology should be used for all assessments throughout the study. Assessments will be done using RECIST, version 1.1. Tumor

assessments will continue to be done after the patient discontinues from the study, until the criteria for progressive disease have been met, or the patient begins another cancer therapy, or withdraws consent.

For the Part 4 dose and schedule evaluation segment, tumor assessments will be performed from evaluation of a CT (chest/abdomen/pelvis) or an MRI scan obtained within 10 days of beginning Cycle 1 and approximately every 8 weeks thereafter (e.g. after completing the infusions of Cycles 2, 4, 6, etc).

4.1.7 **Adverse events**

An adverse event (AE) is any untoward medical occurrence in a patient administered a study drug, and that does not necessarily have a causal relationship with the study drug. (An AE can be any unfavorable and unintended sign or symptom, or disease temporally associated with the use of a study drug, whether or not related to the study drug.) Adverse events include any symptom, physical sign, syndrome or disease which either occurs during the study, having been absent at baseline, or, if present at baseline, appears to worsen during the course of a clinical trial, after starting treatment, whether considered treatment related or not.

Events involving adverse drug reactions, illnesses with onset during the study, or exacerbations of pre-existing illnesses should be recorded. Exacerbation of a pre-existing illness is defined as a manifestation (sign or symptom) of the illness that indicates a significant increase in the severity of the illness as compared to the severity noted at the start of the study. It may include a worsening or increase in severity of signs or symptoms of the illness, increase in the frequency of signs and symptoms of an intermittent illness, or the appearance of a new manifestation/complication.

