Conditions that the patient experienced before treatment with study drug (Pre-dose symptoms) and any new signs, symptoms, or AEs that occur since starting treatment with study drug (regardless of causality) are to be assessed and recorded. Pre-dose baseline assessments must be performed prior to treatment with TK216. Any baseline symptoms or adverse events noted prior to treatment with TK216 should be recorded as part of the Medical History. The assessment and recording of each symptom or AE must also be described by its duration (start date, time and duration), its severity (mild, moderate, severe, very severe), its relationship to the study medication (unrelated, unlikely or possibly related), whether it influenced the course of the study medication, and whether it required specific therapy.

The severity of signs, symptoms, or AEs is to be determined by using the NCI Common Terminology Criteria for Adverse Events (CTCAE) v 4.03. If a sign, symptom or AE is not included in the toxicity severity grading scale, the intensity of the event will be graded as shown below.

- **mild (grade 1):** Symptoms causing no or minimal interference with usual social and functional activities. Symptoms are usually transient and require no special treatment.
- **moderate (grade 2):** Symptoms causing greater than minimal interference with usual social and functional activities. Symptoms are usually ameliorated by simple therapeutic measures
- **severe (grade 3):** Symptoms causing inability to perform usual social and functional activities. Symptoms traditionally require systemic drug therapy or other treatment
- **very severe (grade 4, life-threatening):** Symptoms causing inability to perform basic self-care functions or require medical or operative intervention to prevent permanent impairment, persistent disability, or death.
- **death related to AE (grade 5)**

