4.1.7.1 Assessment of causal relationship

A medically-qualified investigator must assess the relationship of any AE to the use of study drug, based on available information, using the following guidelines:

- **Not related:** There is not a reasonable causal relationship to the investigational product and the adverse event.
- **Unlikely related:** No temporal association or the cause of the event has been identified, or the drug or biologic cannot be implicated.
- **Possibly related:** There is reasonable evidence to suggest a causal relationship between the drug and adverse event.
- **Related:** There is evidence to suggest a causal relationship, and the influence of other factors is unlikely.

The investigator reports causality, but the sponsor retains the final decision on causality when filing to the FDA.

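### Part 4 lets patients add vincristine to TK216 after progression, but the planned AE and laboratory tables have no split at first vincristine, although the safety objective is TK216 alone

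*Combined protocol and SAP*

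**What the plan says.** All references are to the combined protocol and SAP.

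- **Treatment.** Section 2 sets the general rule: "All patients will be treated until objective tumor progression per RECIST v1.1" (or until another listed reason). Section 2.5 then makes a specific allowance for Part 4: "Vincristine may be administered in parallel with the TK216 infusion following progressive disease after TK216-01 monotherapy". Sponsor consultation is required first.
- **Objective.** The Part 4 secondary objective in section 1.4 reads "Safety and tolerability of TK216 alone as characterized by AE type, severity, timing and relationship to study drug", and also covers laboratory abnormalities. The Part 3 counterpart in section 1.3 is worded differently: "Safety and tolerability of TK216 alone and combined with vincristine as characterized by Adverse Event type".
- **Collection.** Sections 4.1.7.4 and 4.1.7.5 collect SAEs to 28 days after the last study drug, and non-serious AEs at least that long.
- **Analysis.** Sections 9.4 and 10.3 include everyone who received any study drug. They show AE incidence by dose group and system organ class, with further summaries by severity and relationship. Laboratory values are summarised at each post-baseline time point, and section 10.3 adds shift tables of CTCAE grade. Section 10 bases all analyses on the same population.
- **Efficacy.** Sections 9.7 and 10.6 limit best response to the period before progression. Safety has no equivalent limit.

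**The concern.** The protocol itself separates TK216 alone from TK216 with vincristine, and for Part 4 it names only the former. The planned tables are the only summaries that could answer that objective, and as written they cover both treatment periods.

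Section 7.3.5.1 lists vincristine toxicities that would appear in such tables: constipation, alopecia, paresthesias, wrist and foot drop, and mild myelosuppression. If these first appear after the switch, they would count towards the profile of TK216 at 175 mg/m²/day. Section 9 says the results will inform whether the safety profile justifies further study, so the monotherapy profile should be readable from the tables.

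**Working it through.** The documents give no figure for this point, so the check is mainly a comparison of provisions.

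**1. Is the vincristine period inside the safety window?** Yes. Vincristine runs in parallel with continued TK216, and AE collection lasts until at least 28 days after the last study drug, even if study drug means TK216 only.

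**2. Does any grouping variable separate the periods?** No.
- Section 9 defines summary categories by initial dose and duration for Parts 1 to 3. It names no Part 4 category and no vincristine category.
- Applied to Cohort 11, the same logic gives one group: 175 mg/m²/day for 28 days.
- The exploratory analyses in section 9 use TK216 dose, duration and cumulative exposure. They do not mention vincristine.

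**3. Which tables are exposed?**
- *All-causality AE and SAE tables:* fully, for events starting after the switch.
- *Laboratory shift tables:* yes. Section 10.3 does not limit follow-up to the monotherapy period.
- *Laboratory summaries by time point:* mainly later cycles. Part 4 scans take place at baseline and "approximately every 8 weeks thereafter" (section 4.1.6.6). Two 28-day cycles are 2 × 28 = 56 days = 8 weeks, so Cycles 1 and 2 are largely monotherapy unless progression is documented earlier.
- *Related-AE tables:* partly. Section 4.1.7 asks for one rating per event, "its relationship to the study medication (unrelated, unlikely or possibly related", and section 4.1.7.1 says "A medically-qualified investigator must assess the relationship of any AE to the use of study drug". There is no separate rating for vincristine, but the operative text mostly points to TK216 (see the objection).

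**4. Is efficacy touched?** No. Best response is cut at progression, and section 9 ends both PFS and DOR at objective progression (or at death, for PFS). The Part 4 response rule also reproduces. With at least 4 responders of 21, the exact binomial gives P(X ≥ 4 | 0.05) = 0.0189, within the stated one-sided 0.025. P(X ≥ 4 | 0.25) = 0.808 agrees with the stated 80% power. Nothing here changes either figure.

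**5. Scale of one AE row.** Let N be patients treated, m those with the event before any vincristine, and k those whose first such event follows the switch.

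- Pooled incidence = (m + k)/N
- TK216-alone incidence = m/N
- Difference = k/N

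Take N = 21, the approximate evaluable number in section 2.5 (more treated patients lower the result). The values of k below are assumed; the documents give none.

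| k (assumed) | k/21 |
|---|---|
| 0 | 0 |
| 1 | 4.8 points |
| 3 | 14.3 points |
| 5 | 23.8 points |

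This shows what each patient is worth in a table of this size. It does not estimate the effect.

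**6. Can the data support a split?** Yes. Section 4.1.7 says each AE "must also be described by its duration (start date, time and duration". Section 7.4 puts administered doses in the eCRF, and concomitant medication is checked at Cohort 11 visits.

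**The case against.** The strongest reply is that this is table layout, which the plan leaves open throughout. Parts 2 and 3 name both regimens in their objectives, yet sections 9.4 and 10.3 give no split for them either. All analysis is descriptive, and including every treated patient and every event is a usual, conservative safety convention. Listings of all raw and derived data are planned, so a reader could separate events by date. No Part 4 stopping boundary or numerical safety threshold uses these tables, and vincristine is limited to progressed patients after Sponsor consultation.

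Much of this stands: the data are separable, and no formal decision rule is affected. What does not stand is that the text is merely silent. Sections 9.4, 10 and 10.3 state who and what is counted, and followed as written they pool the two periods.

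A reader might infer more than the documents support in four ways.

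- *That related-AE tables are equally contaminated, because section 7 describes both drugs under Study Drugs.* The operative text mostly means TK216. Section 4.1.7.1 refers to the investigational product and allows a lesser rating when another cause is identified. Section 2.6.2 asks whether toxicity is unrelated to TK216. Section 7.5 covers accountability for sponsor-supplied TK216, whereas section 7.3.5.3 takes vincristine from the site pharmacy. Attribution remains imperfect when the two drugs overlap.
- *That the tables will be inflated by a definite amount.* The number of patients who switch is not given.
- *That response or progression endpoints are biased.* They end at progression, before the option opens.
- *That section 2 forbids what section 2.5 allows, so the option is void.* Section 2.5 is a specific exception and would have no purpose otherwise.

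**Conclusion.** The point holds as a modest but real gap in a secondary objective. If any Part 4 patient uses the vincristine option, the all-causality AE and SAE tables, the laboratory shift tables and the later-cycle laboratory time points would describe a mixture of TK216 and TK216 plus vincristine. Related-AE tables are affected less. ORR, PFS and DOR are not affected.

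The size cannot be stated. It is zero if nobody switches, and otherwise at most k/N for a given AE row. The conclusion assumes that the tables are produced as sections 9.4, 10 and 10.3 describe, and that AE collection continues through combined treatment as section 4.1.7 provides.

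**What to change.** Add to sections 9.4 and 10.3, for Part 4, three presentations of AEs and laboratory values, including shift tables:

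- **(a) All events**, required: all treated patients over the whole collection period.
- **(b) TK216 alone**: AEs starting, and laboratory values taken, before the first vincristine dose. Patients who never receive vincristine contribute their whole period.
- **(c) TK216 plus vincristine**: AEs starting or worsening in grade, and values taken, on or after the first vincristine dose. The denominator is the number of patients who switched.

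The split uses AE start dates and dosing records already planned. The documents do not say whether a rise in grade opens a new AE record, so the CRF instructions should confirm that the date of worsening is captured. Sample size, alpha, power and patient visits do not change.

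The cost is an extra set of tables. Late or cumulative TK216 toxicity in patients who switch also leaves table (b), and those patients, all of whom have progressed, have shorter follow-up there. That is why table (a) should be required: it keeps such events visible.
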